11.4 Records Retention

All trial related correspondence, subject records, consent forms, record of the distribution and use of all IP and copies of case report forms should be maintained on file for at least 2 years in the US, and 15 years in Canada, after the last approval of a marketing application in an ICH region and until there are no pending or contemplated marketing applications in an ICH region; or until at least 2 years in the US, and 15 years in Canada, have elapsed since the formal discontinuation of clinical development of the IP. These documents will be retained for a longer period if required by the applicable regulatory requirements or by an agreement with the Sponsor. It is the responsibility of the Sponsor to inform the investigator/institution as to when these documents no longer need to be retained. The investigator must notify the Sponsor prior to destroying trial documentation even after the above-mentioned time has passed.

If the responsible investigator retires, relocates, or for other reasons withdraws from the responsibility of keeping trial records, custody must be transferred to a person who will accept the responsibility. The Sponsor must be notified in writing of the name and address of the new custodian.

12 STUDY MONITORING, AUDITING, AND INSPECTING

12.1 Study Monitoring Plan

Each investigator must adhere to the protocol as detailed in this document and agrees that any changes to the protocol must be approved by the Sponsor, prior to seeking approval from the IRB/Ethics Committee. Investigators' proficiency in observing and scoring ophthalmic observations will be established and documented via review of academic training and experience, prior to examining subjects. Each investigator will be responsible for enrolling only those subjects who have met protocol eligibility criteria. During study conduct, Sponsor and/or its representative will conduct periodic monitoring visits to ensure that the protocol and Good Clinical Practice (GCP) are being followed. The monitors may review source documents to confirm that the data recorded on the electronic case report forms (eCRFs) are accurate. Further details of the trial monitoring (including medical monitoring) will be outlined in a monitoring plan.

The investigator and institution will allow Sponsor, monitors or its representatives and appropriate regulatory authorities direct access to source documents and CRFs to perform this verification. Data Managers will also review data and may interact with site personnel for clarifications.

It is important that the investigator(s) and their relevant personnel are available during the monitoring visits and possible audits or inspections and that sufficient time is devoted to the process.

13 ETHICAL CONSIDERATIONS

This study will be conducted according to the standards of International Council on Harmonization, Good Clinical Practice Guideline, Research Ethics Committee regulations, any applicable government regulations, Trust and Research Office policies and procedures.

This protocol, the ICF, relevant supporting information, and all types of subject recruitment or advertisement information must be submitted to the IRB/Ethics Committee for review and must be approved before the study is initiated. Any amendments to the protocol must also be approved by the IRB/Ethics Committee prior to implementing changes in the study. The investigator is responsible for keeping the IRB/Ethics Committee apprised of the progress of the study, any SAEs, and any changes made to the protocol according to the requirements of the site's IRB.

Appendix 1 Schedule of Assessments

Study Period	Screening Visit	Observation Period										
		Day 1/ Procedure	Day 2	Week 1	Week 4	Month 2 (optional)	Month 3	Month 4.5	Month 6	Month 9	Month 12 / Study Exit	Un-scheduled Visit
Visit Number	1	2	3	4	5	5.1	6	7	8	9	10	
Study Day (D) or Week (W)/ Visit Window	-77 to -7	D1	D2 (+2d)	D8 (+2d)	D30 (±7d)	D60 (±7d)	D90 (±7d)	D135 (±14d)	D180 (±14d)	D270 (±14d)	D360 (±14d)	N/A
Informed Consent	X											
Demographics	X											
Medical/Surgical History	X											
Eligibility Review	X											
Cohort Assignment	X											
Surgery/Study Treatment		X										
Ophthalmic Assessments (To be Conducted in Both Eyes)												
UCVA ^a	X		X	X	X	X	X		X		X	(x)
BCVA (ETDRS) by MR (through phoropter) ^a	X				X	X	X	X	X	X	X	(x)
SD-OCT (Macula)	X						X		X		X	(x)
CCT by Ultrasonic Contact Pachymetry	X			X	X	X	X	X	X	X	X	(x)
Slit Lamp Biomicroscopy	X		X	X	X	X	X	X	X	X	X	(x)
Slit Lamp Photography	X				X	X	X		X	X	X	(x)
Goldmann Tonometry (IOP)	X		X	X	X	X	X	X	X	X	X	(x)
Gonioscopy	X						X		X		X	(x)

[figure not shown]
Study Period	Screening Visit	Observation Period										
		Day 1/ Procedure	Day 2	Week 1	Week 4	Month 2 (optional)	Month 3	Month 4.5	Month 6	Month 9	Month 12 / Study Exit	Un-scheduled Visit
Visit Number	1	2	3	4	5	5.1	6	7	8	9	10	
Study Day (D) or Week (W)/ Visit Window	-77 to -7	D1	D2 (+2d)	D8 (+2d)	D30 (±7d)	D60 (±7d)	D90 (±7d)	D135 (±14d)	D180 (±14d)	D270 (±14d)	D360 (±14d)	N/A
Dilated Fundus Examination	X						X		X		X	(x)
Other Assessments												
Adverse Events		X	X	X	X	X	X	X	X	X	X	X
Prior/Concomitant Medications	X	X	X	X	X	X	X	X	X	X	X	X
Laboratory blood draw (hematology, chemistry)	X								X		X	
Urine Pregnancy ^b	X	X-----X										(x)

[figure not shown]
[REDACTED]; BCVA = best-corrected visual acuity; ETDRS = Early Treatment of Diabetic Retinopathy Study; MR = manifest refraction; IOP = intraocular pressure; N/A = not applicable; PRO = patient reported outcome; SD-OCT = spectral domain-optical coherence tomography; (x) = optional (at the discretion of the investigator); UCVA = uncorrected visual acuity; VA = visual acuity; [REDACTED]

^b. For women of childbearing potential, a urine pregnancy test is to be conducted at the Screening Visit. Thereafter, if the subject misses 2 consecutive menstrual cycles, a urine pregnancy test is to be conducted and followed by a serum pregnancy test if the urine test is positive.

Appendix 2 Best Corrected Visual Acuity

Please refer to the Phoropter Refraction and Best-Corrected Visual Acuity (BCVA) Procedure Manual.

Appendix 5 Intraocular Pressure (IOP)

Please measure IOP with a properly sterilized Goldmann Applanation Tonometer.

1. The patient should be seated comfortably at the Slit Lamp.
2. The instrument should be calibrated by adjusting the height of the tonometer probe before initiating measurement.
3. The patient's eye is topically anesthetized.
4. The patient is asked to fixate on a target while the tonometer probe is gently placed on the cornea.
5. Operator reads the IOP value displayed on the tonometer scale. If necessary, the measurement can be repeated to obtain an average IOP value.

Note: Assessment of IOP by means other than Goldmann tonometry (e. g, air puff tonometer or tonopen) is acceptable in any event where the assessor is unable to capture an accurate measure via Goldmann applanation tonometry (i.e., poor visibility of semicircles or subject mobility issues).

Appendix 6 Gonioscopy

Slit Lamp gonioscopy is performed through a mirror. The part of the angle that is viewed is 180° away from the mirror that is being used. The examiner must remember that the image is a mirror image. The view, unlike that seen with indirect ophthalmoscopy, is not an inverted mirror image. In slit-lamp gonioscopy, the angle seen in the superior part of the temporal mirror is the superior part of the nasal angle.

One can use diffuse illumination, focal illumination with a broad beam, and focal illumination with a narrow beam. It is helpful to vary the type of illumination and the orientation of the light. Subtle findings can best be appreciated in this manner.

Please use the Schaeffer Grading System outlined in table below and note whether any clinical findings such as synechiae are present with corresponding location (i.e., number of clock hours).

Schaeffer Grading System		
Grade 4	45° to 35° angle	Wide open
Grade 3	35° to 20° angle	Wide open
Grade 2	20° angle	Narrow
Grade 1	≤10° angle	Extremely narrow
Slit	0° angle	Narrowed to slit
Grading is Based on the Angular Width of the Angle Recess		

Any observed changes from baseline should be recorded in the source document.

Appendix 7 Ultrasonic/Contact Corneal Pachymetry

[figure not shown]
The ultrasonic pachymeter is based on traditional A-scan ultrasonography.

[figure not shown]
Before turning on the pachymeter, use a sterile alcohol prep pad to clean and sterilize the pachymeter probe. Let the probe tip **completely air dry** prior to use to avoid a chemical corneal abrasion from the residual alcohol. Calibrate the pachymeter, following the manufacturer instructions, before measurement.

[figure not shown]
Anesthetize both eyes. Instruct the subject to gaze straight ahead. Gently touch the **central cornea** with the probe tip, applying as little pressure as possible and **keeping the probe perpendicular** to the cornea during measurement to avoid errors. When the measurement is obtained, the probe should be withdrawn from the cornea and reapplied in the same manner for subsequent measurements.

Take a minimum of **three measurements** for each eye and record them. All three measurements should be consistent and in proximity of one another. Values are recorded in microns.

Note: If an outlier measurement is obtained, which deviates from the overall average of the other consistent values, it is important to repeat the measurement two to three times to confirm the value. Repeated measurements must be consistent in order to be considered a valid result. (Potential sources of error in measuring corneal thickness include holding the probe at an oblique angle to the cornea and measuring away from the central corneal apex, both of which would result in elevated readings of central corneal thickness (because corneal thickness increases from the center to the periphery).

Version 2000

APPENDICES

1 LIST OF ABBREVIATIONS AND DEFINITION OF TERMS

Term	Definition
AE	Adverse Event/Experience
AURN001	Neltependocel and Y-27632
██████████	██████████
BCVA	Best Corrected Visual Acuity
CEC	Corneal Endothelial Cells
CFB	Change from Baseline
CI	Confidence Interval
CRF	Case Report Form
██████████	██████████
ETDRS	Early Treatment of Diabetic Retinopathy Study
FAS	Full Analysis Set
FDA	Food and Drug Administration
GCP	Good Clinical Practice
ICH	International Council on Harmonization
IOP	Intraocular Pressure
IP	Investigational Product
██████████	██████████
LogMAR	Logarithm of the Minimum Angle of Resolution
neltependocel	Allogeneic human corneal endothelial cells
OCT	Optical Coherence Tomography
OD	Oculus Dexter or Right Eye
OS	Oculus Sinister or Left Eye
PPS	Per Protocol Set
PRO	Patient Reported Outcomes
SD-OCT	Spectral Domain Optical Coherence Tomography
SAE	Serious Adverse Event/Experience
TEAE	Treatment Emergent Adverse Event
UCVA	Uncorrected Visual Acuity
UPT	Urine Pregnancy Test
US	United States
VA	Visual Acuity
██████████	██████████
WOCBP	Women of Childbearing Potential
Y-27632	A Rho-kinase inhibitor small molecule drug

2 INTRODUCTION

The purpose of this statistical analysis plan (SAP) is to describe the planned analyses and reporting for protocol ABA-1, Version 5.0, dated the 04-Jun-2024.

This SAP is being written with due consideration of the recommendations outlined in the most recent International Conference on Harmonisation (ICH) E9 Guideline, entitled Guidance for Industry: Statistical Principles for Clinical Trials and the most recent ICH E3 Guideline, entitled Guidance for Industry: Structure and Content of Clinical Study Reports.

This SAP describes the data that will be analyzed and the subject characteristics, efficacy, and safety assessments that will be evaluated. This SAP provides details of the specific statistical methods that will be used. The statistical analysis methods presented in this document will supersede the statistical analysis methods described in the clinical protocol. If additional analyses are required to supplement the planned analyses described in this SAP, they may be completed and will be identified in the clinical study report.

3 TRIAL OBJECTIVES

The primary objective of this trial is to evaluate:

- Efficacy of a single injection of different concentrations of *neltependocel* in combination with Y-27632 (i.e., AURN001), *neltependocel* alone, and Y-27632 alone in subjects with corneal edema secondary to corneal endothelial dysfunction

The secondary objective of this trial is to evaluate:

- Safety and tolerability of a single injection of different concentrations of *neltependocel* in combination with Y-27632 (i.e., AURN001), *neltependocel* alone, and Y-27632 alone in subjects with corneal edema secondary to corneal endothelial dysfunction

4 TRIAL DESIGN

4.1 Description of Trial

This is a multicenter, randomized, double-masked, parallel-arm, dose-ranging, Phase 1/2 study of AURN001 in subjects with corneal edema secondary to corneal endothelial dysfunction. The efficacy and safety of AURN001 will be assessed in a clinical trial setting in North America in adult subjects with corneal edema secondary to corneal endothelial dysfunction. Three doses of AURN001 compared with the 2 components of AURN001 separately (*neltependocel* and Y-27632) will be evaluated to assess the contribution of these 2 elements to the efficacy and safety of AURN001.

This trial will enroll approximately 100 subjects in the 5 treatment arms with approximately 20 subjects per arm. A randomized treatment sequence will be assigned. The sponsor will assess the actual enrollment in each arm on an on-going basis throughout the study to maintain a

randomization ratio of 1:1:1:1:1. The sponsor will make adjustments to the randomized treatment sequence and the number of subjects to be treated in each cohort as needed.

The treatment arms are as follows:

[figure not shown]
Table 1 Treatment Assignment Paradigm

Arm	No. of Subjects	Neltependocel Dose	Y-27632 Dose	Endothelial Polishing?
1	20	1.0×10^6	100 μ M	Yes
2	20	5.0×10^5	100 μ M	Yes
3	20	2.5×10^5	100 μ M	Yes
4	20	None	100 μ M	Yes
5	20	1.0×10^6	None	Yes

This study will have a screening period, a surgery/treatment day during which treatment will be administered, and a 12-month observation period. The primary efficacy analysis will be conducted at Month 6. The study will have up to 10 visits with one optional visit: the Screening Visit (Visit 1, -77 days to -7 days); Surgery/Treatment (Visit 2, Day 1); and Follow-up (Visits 3 through 10, Day 2, Week 1, Week 4, and Months 2 (optional), 3, 4.5, 6, 9, and 12, respectively). Unscheduled visits will be allowed, as deemed necessary by the investigator.

This study will be conducted per the schedule shown in Figure 1.

Figure 1 Study Schematic

Assessments can be found in the Schedule of Assessments in Appendix 1.

4.2 Study Endpoints

4.2.1 Efficacy Endpoints

All ocular assessments will be conducted on both eyes. The efficacy evaluations will be based on measurements of BCVA (using ETDRS), ultrasonic contact pachymetry, [REDACTED]

4.2.1.1 Primary Efficacy Endpoints

- Response, defined as a ≥ 15 -letter improvement (3-line gain) from baseline in best-corrected visual acuity (BCVA) at Month 6

4.2.1.2 Secondary Efficacy Endpoints

- Change from baseline in BCVA at Month 6
- Change from baseline in central corneal thickness (CCT) at Month 6
- Response, defined as a ≥ 15 -letter improvement (3-line gain) from baseline in BCVA at all other timepoints
- Change from baseline in BCVA at all other timepoints
- Change from baseline in CCT at all other timepoints
- Response, defined as a ≥ 10 -letter improvement (2-line gain) from baseline in BCVA at each timepoint

4.2.2 Safety Evaluations

- Incidence and severity of ocular treatment-emergent adverse events (TEAEs)
- Incidence and severity of non-ocular TEAEs
- Loss from baseline in BCVA ≥ 15 letters
- Rescue rate and time to rescue

- Graft rejection

The safety evaluations will be based on adverse event (AE) reporting, laboratory findings (clinical chemistry and hematology), and ophthalmic examinations, including Goldmann tonometry, Slit Lamp biomicroscopy, gonioscopy, dilated fundoscopy, and BCVA (as measured by ETDRS).

4.3 Randomization and Masking

This study will be double-masked and will utilize a randomized treatment sequence model. A computer-generated encrypted read-only randomized treatment sequence schedule will be provided by a biostatistician. The randomized treatment sequence schedule will be managed by unmasked team members responsible for assessing enrollment in each arm to maintain a randomization ratio of 1:1:1:1:1.

4.4 Trial Treatment

Subjects eligible to be treated will receive a single injection of AURN001 (*neltepedocel* with Y-27632), *neltepedocel* alone, or Y-27632 alone into the anterior chamber of the study eye. The dose of *neltepedocel* will be either 1.0×10^6 , 5.0×10^5 or 2.5×10^5 cells; the dose of Y-27632 will be 100 μ M. The total volume of administration will be approximately 300 μ L.

The injection of study treatment into the study eye will be performed under local anesthesia (administration method at the investigator's discretion). After creating a small incision at the corneal limbus, the corneal endothelium will be polished to a diameter of approximately 8 mm. Study treatment will be injected into the anterior chamber using a 27-gauge needle. Immediately after completion of surgery, subjects will lie face down for approximately 3 hours (± 15 minutes).

For detailed instructions, please refer to the Procedure Manual, which includes sponsor observation language.

5 ANALYSIS SETS

5.1 Full Analysis Set

The Full Analysis Set (FAS) will be defined as all randomized subjects who received any amount of study drug during intracameral injection. All subjects in FAS will be analyzed according to the treatment they actually received. The Full Analysis Set will be the primary population for evaluating all efficacy endpoints, subject characteristics, and protocol deviations.

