5.3 Safety Analysis Set

The Safety Analysis Set will be the same as FAS. The safety analysis set will be the primary population for evaluating treatment administration, concomitant medication and safety.

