7.4 Statistical Significance

All statistical testing will be done at the two-sided alpha level of 0.05. As this is a Phase 1/2 study, no adjustments to alpha will be made for the tests of multiple comparisons and multiple endpoints. Statistical analysis will be descriptive.

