7.5 Interim Analysis

As stated in Section 7.1, there will be an interim reporting when all subjects complete the primary endpoint at Month 6. As this analysis is for all subjects completing the primary endpoint, this analysis is considered the study primary efficacy analyses. And hence, there will not be alpha adjustment. All p-values will be judged at 2-sided alpha level of 0.05. All p-values are considered nominal.

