7.6 Statistical Hypothesis

This is a Phase 1/2 study. No formal statistical hypothesis is considered.

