13.1.1 Primary Analysis

For the primary endpoint analysis, number and percentage of responders, with associated 2-sided exact (Clopper-Pearson) 95% confidence intervals (CIs), will be presented by treatment group. Proportion of responders will be compared between treatment groups using a two-sided Fisher's exact test. As stated in Section 7.10, subjects who received any rescue surgeries prior to Month 6 or drop out the study due to any reasons prior to Month 6 or missing data at Month 6 will be imputed as treatment failure (i.e. not improve by ≥ 15 letters).

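### Efficacy in the Full Analysis Set is grouped by treatment received, with no as-randomised analysis planned, so any subject given the wrong arm would change groups in the efficacy comparisons

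*SAP*

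**What the plan says.** SAP 5.1 defines the FAS as "all randomized subjects who received any amount of study drug during intracameral injection". It then fixes the grouping rule, "All subjects in FAS will be analyzed according to the treatment they actually received", and the role of the set: "The Full Analysis Set will be the primary population for evaluating all efficacy endpoints". Protocol 10.5 and the Statistical Methods row of the protocol synopsis state the same grouping rule.

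SAP 5.3 adds "The Safety Analysis Set will be the same as FAS", so a single as-treated rule covers both efficacy and safety.

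For the primary endpoint, SAP 13.1.1 says: "Proportion of responders will be compared between treatment groups using a two-sided Fisher's exact test". SAP 6.2 sets out the contrasts: three combination arms against each of two components, and the components against each other. SAP 13.1.2 plans two sensitivity analyses, one in subjects who complete Month 6 and one in the per protocol set. The per protocol set is a subset of the FAS, and neither analysis is said to use the randomised arm.

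On inferential status, SAP 7.4 says "All statistical testing will be done at the two-sided alpha level of 0.05", SAP 7.5 says "All p-values are considered nominal" and SAP 7.6 says "No formal statistical hypothesis is considered".

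**The concern.** Grouping by treatment received is the normal choice for safety, where the question is what happened after a given exposure. For efficacy, the justification for comparing arms is that membership was settled by randomisation. Under the SAP rule a subject given the wrong product leaves the assigned arm and joins another, so membership depends on an event after randomisation. Both the Fisher comparisons and the ANCOVA contrasts in SAP 13.2 would use that altered grouping.

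Nothing in the plan shows the reader the as-randomised result alongside. The disposition table in SAP 8 does not count subjects whose assigned and received arms differ, so a move between arms might not be visible in the summary tables.

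SAP 7.3 says that the trial is to supply estimates and trends for designing later studies. With about 20 subjects per arm, a single subject carries about 5 percentage points of an arm's response rate, so even one mismatch would show in those estimates.

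**Working it through.** **Inputs from the documents**
- Five arms of about 20 subjects, about 100 in total (SAP 4.1). Check: 5 × 20 = 100, which reproduces the stated total. The plan gives no power calculation to reproduce.
- Two-sided Fisher's exact test (SAP 13.1.1), two-sided alpha 0.05 (SAP 7.4).
- Number of comparisons (SAP 6.2): 3 × 2 + 1 = 7.

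**Inputs assumed**
- The documents give neither response rates nor a rate of wrong-arm dosing. The responder counts below are illustrations: 10 to 12 of 20 in a combination arm, 3 to 5 of 20 in a component arm, with one subject or one swapped pair mismatched.

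**Method.** Start from the as-randomised table a/20 v b/20. Move the mismatched subject or subjects to the arm received, keeping their outcomes, and recompute the difference and the two-sided Fisher p-value.

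| Case | As randomised | Mismatch | As treated |
|---|---|---|---|
| 1 | 10/20 v 3/20, difference 50% − 15% = 35 points, p=0.041 | Swapped pair: combination-arm responder received the component; component-arm non-responder received the combination | 9/20 v 4/20, 45% − 20% = 25 points, p=0.176 |
| 2 | 10/20 v 3/20, 35 points, p=0.041 | Swapped pair, reverse outcomes: combination-arm non-responder received the component; component-arm responder received the combination | 11/20 v 2/20, 55% − 10% = 45 points, p=0.006 |
| 3 | 10/20 v 3/20, 35 points, p=0.041 | Swapped pair with the same outcome | 10/20 v 3/20, unchanged |
| 4 | 12/20 v 5/20, 60% − 25% = 35 points, p=0.054 | One component-arm responder received the combination | 13/21 v 4/19, 61.9% − 21.1% = 40.9 points (from unrounded rates), p=0.012 |
| 5 | 11/20 v 4/20, 55% − 20% = 35 points, p=0.048 | One combination-arm responder received the component | 10/19 v 5/21, 52.6% − 23.8% = 28.8 points, p=0.102 |

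In these examples one mismatched subject moves the difference by about 6 points, and a swapped pair moves it by 10 points or not at all. The direction depends on the outcomes of the subjects who move.

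**Scale.** The planned Clopper-Pearson 95% interval for 10/20 runs from 27.2% to 72.8%, a width of 72.8 − 27.2 = 45.6 points. A shift of 6 to 10 points is small beside that imprecision, but it is a systematic displacement and the interval does not account for it.

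**No mismatch.** If every subject receives the assigned arm, the as-treated and as-randomised tables are the same and the rule has no effect.

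**The case against.** The case on the other side is substantial.

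- **The effect is conditional.** The documents report no dosing error and give no expected rate. Even with one mismatch, the remaining 99 or so subjects stay where they were randomised. This stands. A reader might infer that the primary comparison is no longer a randomised one; the documents do not support that.
- **No confirmatory claim is at risk.** The study is unpowered and descriptive, has no formal hypothesis, and treats its p-values as nominal. This also stands. The p-values above show sensitivity at this sample size; they do not show a breached error rate.
- **Grouping by dose received has a rationale.** With a single injection and masked sites, a mismatch would probably be a supply error unrelated to prognosis, and the trial asks about dose and component contribution. This reduces the likely bias. It supports showing an as-treated analysis, but not having it as the only one.
- **The per protocol run may catch it.** A wrong-product injection would probably be a major deviation. However, SAP 9 leaves the exclusion criteria to a later blinded review, and dropping a subject does not return that subject to the randomised arm.

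Two arguments that would make mismatches look likely should not be used. A reader might infer that product is shipped subject by subject; protocol 6.6 says only that the manufacturer ships it to sites, and the supply format is redacted. A reader might also point to the sponsor's power to adjust the treatment sequence; that changes what is assigned and does not by itself make the treatment received differ from it.

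Protocol 10.5 describes FAS members as eligible where SAP 5.1 says randomised. That is a separate question of membership and should be handled as its own point.

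**Conclusion.** The point holds in a limited form. The primary efficacy population is grouped by treatment received in three places, and neither document plans an efficacy analysis by randomised arm. If a mismatch occurs, the affected contrasts can be biased in either direction: in the illustrations, by about 6 points for one subject and by 0 or 10 points for a swapped pair. If none occurs, nothing changes.

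These sizes rest on assumed responder counts, on 20 subjects per arm, and on one subject or one pair being mismatched. The likelihood of a mismatch cannot be judged from the documents. Because the analysis is descriptive and the p-values nominal, the harm is to the estimates carried into later trial design. Priority: low to moderate.

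**What to change.** - In SAP 5.1, protocol 10.5 and the Statistical Methods row of the protocol synopsis, state that efficacy in the FAS is analysed by randomised arm. The synopsis must be included, or the protocol will contradict itself.
- In SAP 5.3 and the matching protocol text, define the Safety Analysis Set as the same subjects analysed by treatment received.
- In SAP 8, add the number of subjects whose assigned and received arms differ.
- In SAP 13.1.2, add an as-treated efficacy run as a sensitivity analysis, to be done only if there are mismatches.

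Cost: about a sentence in each place, no new data, and no change to sample size or alpha. It is best settled before the Month 6 unmasking. The change leaves randomised but untreated subjects outside the FAS, as now.
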